TITLE PAGE

Clinical Trial Protocol: 922

Protocol Title: Effects of NOV03 on the Tear Film in Subjects with Dry Eye Disease

Protocol Number: 922

Study Phase: 4

Investigational Product Name: Perfluorohexyloctane (NOV03; MIEBOTTM)

IND Number: 130558

Indication: Signs and symptoms of dry eye disease

Investigator: [REDACTED]

[REDACTED]
[REDACTED]
[REDACTED]
[REDACTED]

Sponsor: Bausch & Lomb Incorporated
[name]

Contract Research Organization: NA

IRB/IEC: Miami VA Institutional Review Board

	Date
Original Protocol:	23 rd Jan 2023
Amendment 2:	16 th Oct 2023

Confidentiality Statement

[figure not shown]
This protocol contains confidential, proprietary information of Bausch & Lomb Incorporated. Further dissemination, distribution or copying of this protocol or its contents is strictly prohibited.

SPONSOR APPROVAL PAGE

Protocol Title: Effects of NOV03 on the Tear Film in Subjects with Dry Eye Disease
Protocol Number: 922
Final Date: 16th Oct 2023

This clinical study protocol was authored by [REDACTED].

The following personnel approve this protocol.

INVESTIGATOR'S SIGNATURE

[figure not shown]
Protocol Title: Effects of NOV03 on the Tear Film in Subjects with Dry Eye Disease

Protocol Number: 922

Final Date: 16th Oct 2023

I agree to implement and conduct the study diligently and in strict compliance with the protocol, good clinical practices and all applicable laws and regulations. I agree to maintain all information supplied by Ora and the sponsor in confidence and, when this information is submitted to an Institutional Review Board (IRB), Ethical Review Committee (ERC) or another group, it will be submitted with a designation that the material is confidential.

I have read this protocol in its entirety, including the above statement, and I agree to all aspects.

SPONSOR PERSONNEL

Sponsor:	Bausch & Lomb Incorporated [name]
Sponsor Representative:	[REDACTED]

MEDICAL MONITOR

Medical Monitor:	[REDACTED]
-------------------------	------------

SYNOPSIS

Protocol Title:	Effects of NOV03 on the Tear Film in Subjects with Dry Eye Disease
Protocol Number:	922
Investigational Product:	Perfluorohexyloctane (PFHO; MIEBO™; NOV03)
Study Phase:	4
Primary Objective(s):	Determine the effect of a single instillation of PFHO on the thickness and evaporation rate of the mucus-aqueous layer of the tear film
Exploratory Objective(s):	[REDACTED] [REDACTED]
Overall Study Design:	
This pilot, open label, single-arm, single-center study will consist of 2 study visits in subjects with dry eye disease associated with MGD. A Screening Visit will occur to verify subjects are eligible to participate followed by an Assessment Visit to evaluate tear film parameters at baseline and over approx. 4 hours following a single instillation of PFHO.
 
Screening Visit: At Visit 1, the subjects will complete the informed consent process followed by a screening visit to determine the presence of dry eye and associated MGD, which will include slit-lamp exam, visual acuity (VA), intraocular pressure (IOP), meibomian gland dysfunction (MGD) assessment, Schirmer test, tear film break up time (TFBUT), corneal fluorescein staining (CFS), and ocular surface disease index (OSDI).
 
Assessment Visit: At Visit 2, a slit lamp examination and two baseline tear film assessments will be performed (tear film parameters: mucus-aqueous layer thickness (MALT); mucus-aqueous thinning rate (MALTR); [REDACTED] [REDACTED] Then 1 drop of PFHO will be instilled into both eyes (the study eye will be the eye with the highest corneal fluorescein staining). The above assessments will be repeated at multiple time points up to 4 hours post-instillation (time points: 5±1 min, 15±2 min, 30±2 min, 60±5 min, 120±10 min, 240±10 min). Any adverse events will be recorded.

Structure:	

Duration:	This trial consists of 2 office visits over a period of approximately 2 weeks.
Controls:	None (single-arm study)
Dosage Instillation:	At Visit 2, a designated clinical staff member or the investigator will instill 1 drop of PFHO into each eye.
Summary of Visit Schedule:	
Visit 1 (Day -14 to Day 0): Screening / Informed Consent
 
Visit 2 (Day 1): Tear film parameters before and after PFHO instillation

Measures Taken to Reduce Bias:	NA
Study Population Characteristics:	
Number of Subjects:	Approximately 50 subjects will be screened in order to enroll approximately 30 subjects
Condition/Disease:	Dry eye disease associated with meibomian gland dysfunction
Inclusion Criteria:	
General/Ocular Inclusion Criteria
 
 1. Will be at least 18 years of age at the time of consent. 2. Able to provide written voluntary informed consent. 3. Have a subject-reported history of DED in both eyes for at least 6 months prior to Visit 1. 4. Have Tear film break-up time (TFBUT) <10 sec at Visit 1. 5. Have Meibomian Gland Dysfunction (MGD) defined as total MGD score ≥ 3 (secretion of 5 central glands on lower eyelid will be evaluated, each will be scored from 0-3; 0 = normal, 1 = thick/yellow, whitish, particulate 2 = paste; 3 = none/occluded; total score will range from 0-15) at Visit 1. 6. Have a total corneal fluorescein staining score of ≥ 2 and ≤ 11 (i.e. sum of inferior, superior, central, nasal, and temporal) according to the National Eye Institute (NEI) scale at Visit 1. 7. Have at least one eye that satisfies all criteria for 4-6 above at Visit 1. 8. Is able to fix his/her gaze for a minute, i.e. can see the fixation target and with no nystagmus 9. Is able and willing to follow instructions, including participation in all trial assessments and visits.
Exclusion Criteria:	
General/Ocular Exclusion Criteria
 
 1. Have any clinically significant ocular surface slit-lamp findings at Visit 1 and Visit 2 and/or in the opinion of

	
the Investigator had any findings that may have interfered with trial parameters, including
 
a. history of eye traumab. history of Stevens-Johnson syndromec. active blepharitis or lid margin inflammationd. DED secondary to scarring, irradiation, alkali burns, cicatricial pemphigoid, or destruction of conjunctival goblet cells (as with vitamin A deficiency).e. abnormal lid anatomy that caused incomplete eyelid closuref. abnormal cornea shape (keratoconus)g. corneal epithelial defect or significant confluent staining or filamentsh. history of herpetic keratitis.i. has a pterygium in either eye.j. ocular or periocular rosacea that in the judgement of the Investigator interfered with the trial 
2. Has used any topical ocular steroids treatments, prescription dry eye therapy including varenicline nasal spray, or topical anti-glaucoma medication within 60 days prior to Visit 1.3. Have had a LipiFlow procedure within 1 month prior to Visit 2.4. Have received a permanent punctum plug within 3 months (6 months for dissolvable punctum plugs) prior to Visit 2. Have removed a permanent punctum plug within 1 month prior to Visit 2.5. Have used any eye drops (prescription or artificial tears) and/or TrueTear™ device (intranasal tear neurostimulator) within 24 hours before Visit 2.6. Have active ocular allergies or ocular allergies that are expected to be active during the trial period.7. Have worn contact lenses within 1 month of Visit 1 or anticipate using contact lenses during the trial.8. Have undergone intraocular surgery or ocular laser surgery within the previous 6 months or had any planned ocular and/or lid surgeries over the trial period.9. Have an active ocular or systemic infection (bacterial, viral, or fungal), including fever requiring treatment with antibiotics.10. Is a woman who was pregnant, nursing or planning a pregnancy.11. Is a woman of childbearing potential who is not using an acceptable means of birth control; acceptable methods of contraception included: hormonal (oral,
--	--

	
implantable, injectable, or transdermal contraceptives); mechanical (spermicide in conjunction with a barrier such as a diaphragm or condom); intrauterine device; or surgical sterilization of partner. For non-sexually active females, abstinence could have been regarded as an adequate method of birth control; however, if the subject becomes sexually active during the trial, she must agree to use adequate birth control as defined above for the remainder of the trial.
 
12. Has an uncontrolled systemic disease in the opinion of the Investigator will interfere with the trial.13. Has a known allergy and/or sensitivity to the investigational drug.14. Has used any oral medications known to cause ocular drying (e.g., antihistamines, antidepressants, etc.) on a non-stable regimen within 1 month prior to Visit 1 or is expected to be unstable during the trial.15. Have taken isotretinoin (e.g. Accutane, Myorisan, Claravis, Amnesteem) within 6 months of Visit 1.16. Has corrected VA worse than or equal to logarithm of the minimum angle of resolution (LogMAR), +0.7 as assessed with Early Treatment Diabetic Retinopathy Study (ETDRS) charts in both eyes at Visit 1.17. Is currently enrolled in an investigational drug or device study or had used an investigational drug or device within 60 days of Visit 2.
Study Formulations:	Test Article: Perfluorohexyloctane
Efficacy Measures and Endpoints:	
Primary Efficacy Measures
 
• Mucus-aqueous layer thickness (MALT) and thinning rate (MALTR) at baseline and at multiple time points following instillation of PFHO 
[REDACTED]
 
[REDACTED]
 
[REDACTED]
 
[REDACTED]

Safety Measures:	
• Adverse Events (AEs; reported, elicited and observed)
General Statistics	Continuous variables will be summarized using the mean, standard deviation, median, minimum, and maximum. Categorical variables will be summarized using frequencies and percentages.
Analysis Populations	

Full Analysis Set (FAS): The FAS will consist of all enrolled subjects who are instilled with study drug
Per Protocol Set (PP Set): The PP Set will consist of FAS subjects with no protocol violations expected to affect the evaluability of efficacy.

Safety Analysis

The number and percentage of subjects with specific treatment-emergent adverse events (TEAEs) will be summarized for each treatment group. The number of subjects will be tabulated by MedDRA System Organ Class and preferred term within each system organ class.

Primary Efficacy Analyses

The primary comparison in this trial is CFB in MALTR and MALT following a single instillation of PFHO. Change from baseline (post-instillation minus baseline, average of 2 baseline readings) at each post instillation time point will be summarized using continuous summary statistics.

Hypotheses

For each primary endpoint at each post-instillation timepoint, the null hypothesis is that the mean change from baseline is zero. The alternative hypothesis is that the mean change from baseline is not zero.

Methods

Each primary endpoint will be summarized by post-instillation timepoint using continuous summary statistics for the FAS. Paired t-tests will be used to test the statistical hypotheses. Each null hypothesis will be rejected if the corresponding two-sided p-value is less than 0.05.

Sample Size Calculations

A sample size of 30 subjects will have 80% power to detect a difference in means of 0.529 times the standard deviation of the paired differences, using a paired t-test with a 5% two-sided significance level.

Summary of Known and Potential Risks and Benefits to Human Subjects

Refer to MIEBO Prescribing Information (Appendix 3).

TABLE OF CONTENTS

Title Page.....	1
Sponsor Approval Page	2
Investigator's Signature.....	3
SPONSOR PERSONNEL	4
SYNOPSIS	5
TABLE OF CONTENTS	10
LIST OF ABBREVIATIONS.....	13
1 INTRODUCTION.....	15
2 STUDY OBJECTIVES	16
3 CLINICAL HYPOTHESES.....	16
4 OVERALL STUDY DESIGN	16
5 STUDY POPULATION.....	17
5.1 Number of Subjects (approximate).....	17
5.2 Study Population Characteristics.....	17
5.3 Inclusion Criteria.....	17
5.4 Exclusion Criteria	18
5.5 Withdrawal Criteria (if applicable).....	19
6 STUDY PARAMETERS.....	19
6.1 Efficacy Measures and Endpoints.....	19
6.1.1 Primary Efficacy Measure(s) and Endpoints	19
6.1.2 Secondary Efficacy Measure(s) and Endpoints	19
6.1.3 Exploratory Efficacy Measure(s) and Endpoints	19
6.2 Safety Measures	19
7 STUDY MATERIALS	19
7.1 Study Treatment(s).....	19
7.1.1 Study Treatment.....	19
7.1.2 Instructions for Use and Administration.....	20
7.2 Other Study Supplies	20
8 STUDY METHODS AND PROCEDURES	20
8.1 Subject Entry Procedures.....	20
8.1.1 Overview.....	20
8.1.2 Informed Consent.....	20

CFS	Corneal Fluorescein Staining
CRF	case report form
DED	Dry Eye Disease
ETDRS	Early Treatment of Diabetic Retinopathy Study
FDA	Food and Drug Administration
FAS	Full Analysis Set
GCP	Good Clinical Practice
GLP	Good Laboratory Practice
GMP	Good Manufacturing Practice
HIPAA	Health Insurance Portability and Accountability Act
IB	Investigator's brochure
IBI	Inter-Blink-Interval
ICF	informed consent form
ICH	International Conference on Harmonisation
IEC	Independent Ethics Committee
IOP	Intraocular pressure
IP	investigational product
IRB	institutional review board
ITT	intent to treat
LBUT	Lipid Break Up Time
LLT	Lipid Layer Thickness
LMU	Lipid Map Uniformity
MALT	Muco-Aqueous Layer Thickness
MALTR	rate of change of the MALT value
MedDRA	Medical Dictionary for Regulatory Activities
MGD	Meibomian Gland Dysfunction
NEI	National Eye Institute
NOV03	Development name for perfluorohexyloctane (MIEBO)
OD	right eye
OS	left eye
OU	both eyes
OSDI [®]	Ocular Surface Disease Index
PP	per protocol
SAE	Serious Adverse Event
SAF	Safety Analysis Set
SAP	statistical analysis plan

SD	standard deviation
SDC	Statistics and Data Corporation
SOP	standard operating procedure
TEAEs	Treatment-emergent Adverse Events
TFBUT	Tear Film Break-up Time
VA	Visual Acuity

1 INTRODUCTION

Dry eye disease (DED) is a common ocular condition with approx. 18 million currently diagnosed with the disease in the US, and with many more people remaining undiagnosed (Farrand, et al. 2017; MarketScope 2020). Typical clinical signs of DED include decreased tear fluid, tear film instability, and ocular surface damage with associated symptoms of dryness, grittiness, burning, stinging, light sensitivity, and blurred vision (Bartlett, et al. 2015; Craig, et al. 2017). Previously, DED was characterized into 2 main types, aqueous deficient (in which lacrimal secretion is reduced) or evaporative (in which evaporation of aqueous from the tear film is excessive) (Bron, et al. 2017; Craig, et al. 2017). It is now recognized that DED is on a continuum and that the most common cause of the disease is excessive evaporation due to conditions such as meibomian gland dysfunction (MGD), a reduced blink rate (for example due to long-term use of digital displays), certain drugs, contact lens use, and some eyelid disorders (Craig, et al. 2017). The most common cause of evaporative DED is MGD, which is present in approx. 9 out of 10 patients with the disease (Lemp, et al. 2012; Rabensteiner, et al. 2018; Badian, et al. 2021). MGD results in thinning of the tear film lipid layer leading to excessive evaporation of the underlying aqueous layer and associated tear film instability, hyperosmolarity, desiccation stress, and loss of mucin-producing goblet cells, which all cascade into a continuing cycle of inflammation and ocular surface damage (Baudouin, et al. 2016; Craig, et al. 2017).

Current prescription DED therapies are aimed at reducing inflammation or increasing tear secretion but are not directly targeted at the main root cause of DED, namely excessive evaporation. Perfluorohexyloctane ophthalmic solution (PFHO; trade name MIEBOTTM; development name NOV03) is an FDA approved, water-free, non-steroidal, preservative-free eye drop indicated for treatment of the signs and symptoms of DED. PFHO belongs to a unique class of compounds known as semifluorinated alkanes which have low surface tension and amphiphilic properties due to a lipophobic/aerophilic fluorinated segment and a lipophilic hydrocarbon segment (Meinert and Roy 2000). PFHO is thought to act as a functional replacement for the lipid layer by spreading rapidly over the ocular surface to form a long-lasting, anti-evaporative barrier (Agarwal, et al. 2018; Krosser 2018; Borchman 2022). Therefore, PFHO may prevent excessive evaporation of the aqueous component of the tear film in patients with evaporative DED, thus reducing the signs and symptoms of DED as has been consistently demonstrated in both a Phase 2 study and 2 Phase 3 clinical studies (Tauber, et al. 2021; Sheppard 2022; Tauber, et al. 2022).

To date, the effect of PFHO on inhibiting evaporation *in vivo* has not been demonstrated and there is limited available information regarding how PFHO modulates the lipid and aqueous tear film layers; in addition, demonstration of inhibition of evaporation by PFHO is currently limited to *in vitro* data. The Tear Film Imager (AdOM, Advanced Optical Technologies Ltd, Lod, Israel) combines spectrometry and imaging to quantitatively assess changes in the tear lipid and aqueous layers with nanometer resolution. There are 6 tear film parameters which are measured simultaneously with the TFI:

1. MALT: the average Muco-Aqueous Layer Thickness in nanometer resolution
2. MALTR: the rate of change of the MALT value in nm/sec, as measured in the steady state phase of a representative blink
3. LLT: the average Lipid Layer Thickness in nanometer resolution
4. LBUT: the Lipid Break Up Time (in sec) which strongly correlates to tear breakup time
5. IBI: the average Inter-Blink-Interval (in sec).
6. LMU: the average Lipid Map Uniformity measured on the Lipid map taken about 1 second after the blink which allows quantitation of the spatial variation of lipid across the cornea.

Several studies have been published which evaluated tear film parameters with the TFI. Cohen et al used the TFI to demonstrate that the distribution of lipid in eyes with DED is nonuniform and has more variance over the corneal surface as compared to normal eyes and hypothesized that this nonuniformity may be the cause of increased evaporation of the aqueous tear film layer in DED (Cohen, et al. 2020). In addition, the parameters of MALT and LBUT have been shown to be significantly thinner and shorter, respectively, in patients with DED vs controls (Segev, et al. 2020). Data from a recent study has also demonstrated correlation of specific tear film parameters with certain DED symptoms and/or signs (Arita, et al. 2022). Lastly, unpublished pilot data suggests that PFHO may decrease the MALTR and thus the rate of evaporation in a subject with evaporative DED.

2 STUDY OBJECTIVES

The primary objective is to test the hypotheses (twelve) that the effects of a single instillation of PFHO in the study eye on the thickness and evaporation rate of the mucus-aqueous layer of the tear film at six time points between 5 minutes and 4-hours (5 ± 1 min, 15 ± 2 min, 30 ± 2 min, 60 ± 5 min, 120 ± 10 min, 240 ± 10 min) after instillation are nominally statistically significant in adults with established currently untreated bilateral dry eye disease associated with meibomian gland dysfunction who are not recent users of contact lenses or any medication that could affect ocular dryness.

3 CLINICAL HYPOTHESES

It is hypothesized that PFHO will increase MALT and decrease MALTR in a population of subjects with dry eye disease associated with MGD.

[figure not shown]
4 OVERALL STUDY DESIGN

This is a pilot, open label, single arm study.

The study will consist of 2 study visits: a Screening Visit to verify subjects are eligible to participate and an Assessment study visit to evaluate tear film parameters at baseline and over approx. 4 hours following a single instillation of PFHO (Figure 1).

At Visit 1, the subjects will complete the informed consent process followed by a screening visit to determine the presence of dry eye and associated MGD, which will include slit-lamp exam, visual acuity (VA), IOP, MGD assessment, Schirmer test, TBUT, CFS, OSDI. At Visit 2, a slit lamp examination will be performed. After 20 min, a baseline examination will be conducted by performing a Tear Film Imager assessment in the study eye (tear film parameters measured twice 20-40 min apart; study eye = worst CFS eye at baseline). The study eye drop will then be applied to both eyes. Tear film imager assessments will then be performed in the study eye at multiple time points up to 4 hours post-instillation as shown in Figure 1.

Figure 1: Study Design Schematic

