5.3 Inclusion Criteria

General/Ocular Inclusion Criteria

1. Will be at least 18 years of age at the time of consent.
2. Able to provide written voluntary informed consent.
3. Have a subject-reported history of DED in both eyes for at least 6 months prior to Visit 1.
4. Have Tear film break-up time (TFBUT) <10 sec at Visit 1.
5. Have Meibomian Gland Dysfunction (MGD) defined as total MGD score ≥ 3 (secretion of 5 central glands on lower eyelid will be evaluated, each will be scored from 0-3; 0 = normal, 1 = thick/yellow, whitish, particulate 2 = paste; 3 = none/occluded; total score will range from 0-15) at Visit 1.
6. Have a total corneal fluorescein staining score of ≥ 2 and ≤ 11 (i.e. sum of inferior, superior, central, nasal, and temporal) according to the National Eye Institute (NEI) scale at Visit 1.
7. Have at least one eye that satisfies all criteria for 4-6 above at Visit 1.
8. Is able to fix his/her gaze for a minute, i.e. can see the fixation target and with no nystagmus
9. Is able and willing to follow instructions, including participation in all trial assessments and visits.

Confidential

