6 STUDY PARAMETERS

6.1 Efficacy Measures and Endpoints

6.1.1 Primary Efficacy Measure(s) and Endpoints

- Change from baseline in mucus-aqueous layer thickness (MALT) and thinning rate (MALTR) for study eyes at 5 ± 1 min, 15 ± 2 min, 30 ± 2 min, 60 ± 5 min, 120 ± 10 min, and 240 ± 10 min following instillation of NOV03

6.1.2 [REDACTED]

[REDACTED]

[REDACTED]

[REDACTED]

[REDACTED]

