10 STATISTICS

10.1 Assessment of Efficacy

Efficacy evaluations will be completed using the Full Analysis Set.

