10.5 Protocol Deviations

All protocol deviations will be reported to the sponsor and recorded throughout the study. A tabulation of protocol deviations (including categorizations of major and minor) will be presented.

Important protocol deviations leading to exclusion from the Per-Protocol Population will include the following.

- Ineligibility
- Missing primary endpoint data at any time point at Visit 1
- Use of any prohibited medication potentially affecting the primary endpoint at Visit 1

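### The study eye is chosen on corneal staining alone, so the only eye imaged can fail inclusion criteria 4-6 while the eye that qualified the subject is not measured

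*Combined protocol and SAP*

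**What the plan says.** **Eligibility is set at eye level, and one eye is enough.** Section 5.3, criterion 7: "Have at least one eye that satisfies all criteria for 4-6 above at Visit 1". Criteria 4-6 are break-up time under 10 s, an MGD score of at least 3, and a total NEI staining score from 2 to 11. Criterion 5 also serves as the trial's definition of the disease: "Have Meibomian Gland Dysfunction (MGD) defined as total MGD score ≥ 3".

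**The study eye is set by staining only.** Synopsis, Overall Study Design: "the study eye will be the eye with the highest corneal fluorescein staining". Section 4: "study eye = worst CFS eye at baseline". Neither mentions criteria 4-6.

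**Only the study eye is imaged and analysed.** Section 4: "Tear film imager assessments will then be performed in the study eye at multiple time points". Section 6.1.1 defines the primary endpoints as change from baseline in "mucus-aqueous layer thickness (MALT) and thinning rate (MALTR) for study eyes". Section 10.1: "Efficacy evaluations will be completed using the Full Analysis Set".

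**Per-protocol exclusions.** Section 10.5 introduces its list with "Important protocol deviations leading to exclusion from the Per-Protocol Population will include the following", and the list includes ineligibility.

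**The concern.** Criterion 7 anticipates subjects with one qualifying and one non-qualifying eye. In such a subject the staining rule can pick the wrong one, because two of the three eye-level criteria play no part in the choice. The third has an upper limit, and a highest-score rule runs directly against it.

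No later step catches this. The subject is eligible under criterion 7, so the per-protocol exclusion for ineligibility does not apply. The Full Analysis Set takes everyone who received the drop. The eye therefore enters all twelve primary tests listed in Section 2 (two endpoints at six times).

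The clearest case is an eye with an MGD score below 3. Sections 2 and 3 are about dry eye associated with MGD, and this would be an eye without MGD by criterion 5, measured in place of an eye with it. Staff who sensibly imaged the qualifying eye instead would be departing from the written rule.

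**Working it through.** **1. Can it happen?** Apply the rules to one subject:

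| | Staining (2-11) | MGD score (≥3) | Break-up time (<10 s) | Meets 4-6? |
|---|---|---|---|---|
| Right eye | 6 | 5 | 6 s | Yes |
| Left eye | 8 | 1 | 6 s | No (criterion 5) |

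The right eye makes the subject eligible. The left eye has the higher staining, so it becomes the study eye. There are two routes to this outcome:

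- (a) The higher-staining eye scores 11 or less but fails criterion 4 or 5.
- (b) The higher-staining eye scores above 11 and so fails criterion 6.

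Enumerating all two-eye profiles (staining 0-15, with 15 an assumed maximum; MGD 0-15; break-up time pass or fail) found both: 22,230 profiles by route (a) and 33,280 by route (b), out of 116,220 eligible profiles. These counts show that the case exists. They are not frequencies.

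**2. How often?** The documents give no between-eye data, so every input here is an assumption: between-eye correlation 0.5 to 0.85; correlation among the three signs within an eye 0 to 0.5; staining mean 4-7, SD 2-3; median break-up time 4-6 s, log SD 0.4-0.5; MGD mean 4-8, SD 3. There were 300,000 simulated subjects per scenario, and tied eyes were counted as correctly chosen. The quantity is P(higher-staining eye fails 4-6 | at least one eye meets them).

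| Within-eye correlation | All eligible | Also dropping subjects with any eye above 11 |
|---|---|---|
| 0 | 1.3-25.1% | 1.3-18.7% |
| 0.3 | 0.6-20.3% | 0.6-12.2% |
| 0.5 | 0.3-17.4% | 0.3-8.4% |

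The last column is a rough stand-in for exclusion 1, which removes significant confluent staining but sets no score limit. In a sample of 30:

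- lowest: 0.003 × 30 = 0.1 subjects
- highest: 0.25 × 30 = 7.5, or 0.187 × 30 = 5.6 with the stand-in
- middle inputs (between-eye 0.7; within-eye 0.3; staining mean 5, SD 2.5; median break-up time 5 s; MGD mean 6): about 4.6%, or 0.046 × 30 = 1.4

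**3. What would it cost in power?** First, the plan's own figure (Section 10.8.2): n = 30, effect 0.529 SD, two-sided 5%. The noncentrality is 0.529 × √30 = 2.897 on 29 degrees of freedom, with critical value 2.045. The noncentral t gives power 0.7997, which matches the stated 80%.

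Now let k of the 30 study eyes have a fraction r of the planned response, with the SD unchanged: d = 0.529 × (30 − k(1 − r)) / 30.

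| k | r = 0: d | Power | r = 0.5: d | Power |
|---|---|---|---|---|
| 1 | 0.511 | 77% | 0.520 | 79% |
| 3 | 0.476 | 71% | 0.503 | 76% |
| 7 | 0.406 | 57% | 0.467 | 70% |

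If r = 1, power stays at 80% for any k.

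**The case against.** The wording gap itself is hard to dispute. The case on the other side is that it matters little.

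- *The size rests on assumptions.* True. The 25% needs the lowest between-eye correlation, no correlation among signs and the most adverse marginals; middle inputs give about 4.6%. The row with seven eyes and 57% power is a tail illustration and should carry no weight as a forecast.
- *Zero response is implausible.* Largely fair. Section 1 describes the drop as forming a barrier over the ocular surface, and nothing says an eye that misses one cut-off would not respond. In the example above the chosen eye fails only the MGD score. The loss may be nil.
- *Criterion 3 requires disease in both eyes.* It requires a subject-reported history of dry eye in both, which does not make both meet criteria 4-6.
- *Exclusion 1 removes heavily stained eyes.* It may remove some route (b) cases. It does not touch route (a).
- *Section 10.1.5 provides for fellow-eye summaries.* Only where both eyes were recorded. It schedules no imaging of the fellow eye.
- *This is a single-arm pilot with nominal p-values, and every enrolled subject has the disease at subject level.* True, and it limits the consequence. It does not explain why a non-qualifying eye should be measured when a qualifying one is present.
- *Appendices 1 and 2 and Figure 1 were not available for this review.* A clarifying rule there cannot be ruled out. The Synopsis and Section 4 would still need to agree with it.

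**Conclusion.** The concern holds. Followed exactly, the plan can measure an eye that fails its own eye-level criteria, including its definition of MGD, and leave a qualifying eye in the same subject unmeasured. This follows from the text of the Synopsis and Sections 4, 5.3 and 6.1.1 and needs no numerical assumption.

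The size is uncertain. Frequency is unknown; on assumed inputs it runs from well under one subject in 30 to several, with one or two a reasonable middle. The effect on power runs from none to a few points in that middle range. Neither the validity of the t-tests nor the eligibility of the subjects is in question. It should be fixed because the gap is clear and closing it is free, not because a loss of power has been shown.

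**What to change.** Replace the study-eye wording in the Synopsis and in Section 4 with:

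> *The study eye is the eye that meets inclusion criteria 4-6 at Visit 1. If both eyes meet them, it is the eye with the higher total NEI corneal staining score at Visit 1; if the totals are equal, it is the right eye.*

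This also settles two smaller points. Sections 8.3.1.1 and 8.3.1.2 list staining at Visit 1 but not at Visit 2, so the reference to baseline in Section 4 should be to Visit 1. The supplied text also has no rule for equal scores; the right eye is an arbitrary convention, and any rule fixed in advance would serve. If Appendix 1, Appendix 2 or Figure 1 states a study-eye rule, it should be brought into line.

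The cost is one sentence in each of two places. The data are already collected at Visit 1, and no subjects, visits or procedures are added. The sample size of 30 and the stated 80% power are unchanged.
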